Continuous data will be described using descriptive statistics (i.e. n, mean, standard deviation, median, minimum, and maximum). Categorical data will be described using the subject count and percentage in each category. For the summary statistics of all numerical variables unless otherwise specified, minimum and maximum will be displayed to the same level of precision as reported. Mean and median will be displayed to one level of precision greater than the data collected. Standard deviation / standard error will be displayed to two levels of precision greater than the data collected. P-values will be rounded to three decimal places. If a p-value is less than 0.001 it will be reported as “<0.001.” If a p-value is greater than 0.999 it will be reported as “>0.999.” Data will be displayed in all listings sorted by treatment group.

Subjects will be identified in the listings by the subject identification number concatenated with the investigator number.

When count data are presented, the percentage will be suppressed when the count is zero in order to draw attention to the non-zero counts. A row denoted “Missing” will be included in count tabulations where specified on the shells to account for dropouts and missing values. The denominator for all percentages will be the number of subjects in that treatment within the analysis population of interest, unless otherwise specified.

Unless otherwise specified, baseline will be defined as the last non-missing evaluation prior to or on the date of treatment injection (Day 1). The study day will be calculated as assessment date – date of treatment injection (Day 1) + 1.

For all efficacy and safety analyses, analysis visit windows will be used for assigning assessments to an analysis visit, as follows:

| Scheduled Visit | Target Day | Visit Window (Days) |
|-----------------|------------|---------------------|
| Screening | -30 to -1 | Not applicable |
| Day 1 | 1 | Not applicable |
| Day 7 | 7 | 5 to 9 |
| Day 28 | 28 | 25 to 31 |
| Month 2 | 60 | 53 to 67 |
| Month 3 | 90 | 83 to 97 |
| Month 6 | 180 | 152 to 208 |
| Month 9 | 270 | 242 to 298 |
| Month 12 | 360 | 332 to 388 |
| Month 18 | 540 | 512 to 568 |
| Month 24 | 720 | 692 to 748 |
| Month 30 | 900 | 872 to 928 |
| Month 36 | 1080 | 1052 to 1108 |

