Only those assessments which are assigned to an analysis visit will be included in the summary tables and figures which are presented by visit. For summaries of an event at or before a given time point, such as recurrence at Month 12, all assessments (including unscheduled visits) on or before the upper limit of the corresponding visit window will be considered. All assessments will be presented in the data listings.

For summaries presented by 3 month time intervals through Month 12, the intervals will be defined based on study days and the analysis visit windows, as follows:

- Day 1 to 3 months: day 1 to day 97 (upper limit of Month 3 visit window)
- 3 to 6 months: day 98 to day 208 (upper limit of Month 6 visit window)
- 6 to 9 months: day 209 to day 298 (upper limit of Month 9 visit window)
- 9 to 12 months: day 299 to day 388 (upper limit of Month 12 visit window)

For summaries presented by 6 month time intervals, the intervals will be defined based on study days and the analysis visit windows, as follows:

- Day 1 to 6 months: day 1 to day 208 (upper limit of Month 6 visit window)
- 6 to 12 months: day 209 to day 388 (upper limit of Month 12 visit window)

- 12 to 18 months: day 389 to day 568 (upper limit of Month 18 visit window)
- 18 to 24 months: day 569 to day 748 (upper limit of Month 24 visit window)
- 24 to 30 months: day 749 to day 928 (upper limit of Month 30 visit window)
- 30 to 36 months: day 929 to day 1108 (upper limit of Month 36 visit window)

The Month 6 analysis will include all assessments (events, medications, etc.) with a start day on or before the upper limit of the Month 6 visit window (study day 208). The Month 12 analysis will include all assessments (events, medications, etc.) with a start day on or before the upper limit of the Month 12 visit window (study day 388). The analysis at Month 36 will include all data in the database.

For tabulations of data on the Safety population, subjects who were randomized but did not receive treatment will not be included; however data for all subjects in the Safety population will be included in the data listings. In the listings, subjects who did not receive treatment will be grouped separately by their randomized treatment assignment (i.e., FAI Insert - Not Treated, Sham Injection - Not Treated). Percentages for Safety population summaries will be based on the total number of subjects who receive treatment.

All analyses will be conducted using SAS Version 9.2 or higher.

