8.1. Primary Efficacy Endpoint

[figure not shown]
The primary efficacy endpoint is defined as the proportion of subjects who have a recurrence of uveitis in the study eye within 6 months following treatment. As noted in section 4, all recurrence assessments (including unscheduled visits) on or before the upper limit of the 6 month visit window (Day 208) will be considered. Recurrence is captured on the Recurrence of Uveitis eCRF page and, for the US/FDA, is defined as:

- An increase in the vitreous haze of ≥ 2 steps ([Nussenblatt 1985](#)), compared to baseline or any visit time point prior to Month 6
OR
- A deterioration in visual acuity of at least 15 letters BCVA associated with recurrence of uveitis, compared to baseline or any visit time point prior to Month 6

Any criterion used to define recurrence must be attributable only to non-infectious uveitis. To prevent post-procedural inflammatory reactions from being reported as uveitis recurrences, assessments for recurrence of uveitis will begin after the study Day 7 visit.

The definition of a ≥ 2 step increase in vitreous haze is detailed in the diagram below.

Vitreous Haze: ≥ 2 step increase

* Nussenblatt et al 1985

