8.1.1. Primary Analysis

The primary efficacy analysis will be performed on the ITT population at 6 months and will compare the proportion of subjects, in the treatment and control groups, who do not have a recurrence of uveitis in the study eye (as defined above) in the 6 months following Day 1.

The primary efficacy analysis will be conducted after all subjects in the study have completed 6 months of treatment or have discontinued study participation.

The number and percentage of subjects with no recurrence of uveitis in the study eye will be presented by treatment group. A continuity-corrected Chi-square test will be used to assess the statistical significance of a difference between treatment groups in the primary efficacy analysis. Mathematically stated:

$$H_0: 6 \text{ Month Recurrence Free Rate}_{FAI} = 6 \text{ Month Recurrence Free Rate}_{Sham}$$

$$H_1: 6 \text{ Month Recurrence Free Rate}_{FAI} \neq 6 \text{ Month Recurrence Free Rate}_{Sham}$$

The odds ratio for no recurrence (FAI insert/sham) and 95% confidence interval will also be presented.

Although the primary analysis will be performed on both the FDA and ROW definitions of recurrence, no adjustment of type I error will be performed as the FDA and ROW primary efficacy endpoint analyses will be independently evaluated.

The same inferential analysis employing the same methods as for the primary analysis will be performed for the PP population to assess recurrence at Month 6. Additionally, the same analysis will be performed for both the ITT and PP populations to assess recurrence in the exploratory analyses conducted at Months 12 and Month 36. For Month 12, any recurrence at or before the end of the 12 month visit window (Day 388) will be counted. For Month 36, any recurrence at or before the end of the 36 month visit window (Day 1108) will be counted. No adjustment of type I error will be performed as these analyses are considered supportive to the primary analysis.

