For each subject and eye (study, fellow), the number of recurrences through Month 6, 12 and 36 will be calculated. Recurrences imputed at Month 6, 12 or 36 due to missing data as per [Section 8.1.2](#) will be considered a recurrence for this calculation. The number of recurrences per subject and eye (study, fellow) will be described using descriptive statistics as well as the number and percentage of subjects by category (0, 1, 2, 3, 4, 5, >5). Additionally the total number of recurrences summed across all subjects, all study eyes and all fellow eyes will be presented by treatment group.

The time to first recurrence of uveitis within 6 months is calculated as the number of days between the date of injection (Day 1) and the visit date of the first reported recurrence of uveitis in the study eye. Subjects who do not experience a recurrence of uveitis within 6 months will be censored at the date of their Month 6 visit. The time to first recurrence of uveitis within 12 (or 36) months will be calculated in a similar manner, censoring at the date of a subject's Month 12 (or 36) visit if the subject does not experience a recurrence of uveitis within 12 (or 36) months. Recurrences imputed at Month 6 (or Month 12 or Month 36) due to missing data as per [Section 8.1.2](#) will be considered a recurrence in the time to recurrence analysis. Median time to recurrence and the 95% confidence interval for the median will be summarized by treatment group and randomization strata. The Kaplan-Meier estimated probabilities of recurrence will also be presented for monthly intervals through 36 months. Since time to recurrence is calculated in days, the monthly intervals will be defined based on 30 days = 1 month. Kaplan-Meier plots for time to first recurrence of uveitis will also be presented.

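### SAP 8.2 censors event-free subjects at their own Month 6, 12 or 36 visit but counts recurrences to the end of the visit window, so the end of each Kaplan-Meier curve overstates recurrence in both arms

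*SAP*

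**What the plan says.** SAP 8.2 dates a recurrence at the visit that first reports it. For event-free subjects the rule is "Subjects who do not experience a recurrence of uveitis within 6 months will be censored at the date of their Month 6 visit", and for the later analyses it is "censoring at the date of a subject's Month 12 (or 36) visit".

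Events follow a different limit. SAP Section 4 sets the general rule for events by a time point: "all assessments (including unscheduled visits) on or before the upper limit of the corresponding visit window will be considered". SAP 8.1 repeats it for Month 6: "all recurrence assessments (including unscheduled visits) on or before the upper limit of the 6 month visit window (Day 208) will be considered". SAP 8.1.1 does so for Month 12, "any recurrence at or before the end of the 12 month visit window (Day 388) will be counted", and gives Day 1108 for Month 36.

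The window table in SAP Section 4 reads "Month 6 | 180 | 152 to 208" and "Month 12 | 360 | 332 to 388". Each window is 57 days wide (208 - 152 + 1 = 57).

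On reporting, SAP 8.2 says: "Median time to recurrence and the 95% confidence interval for the median will be summarized by treatment group and randomization strata". It adds plots and Kaplan-Meier probabilities on a 30-day grid, so tabulated Month 6 is Day 180. Recurrences imputed for missing data count as events, but no event date is given for them. The endpoint is listed as exploratory and descriptive.

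**The concern.** A subject seen event-free on Day 160 leaves the risk set that day. The same subject with an unscheduled flare on Day 195 stays at risk until Day 195 and counts as an event. Risk-set membership then depends on the outcome, which breaks the non-informative censoring that Kaplan-Meier needs. This is not loss to follow-up, because protocol 9.17 follows all randomized subjects for as long as they agree to return.

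Unscheduled visits are not required for the problem. Events and censoring both fall on visit dates spread over the window, so subjects seen early and event-free are removed before late visitors are examined. Each recurrence found at a late visit is divided by a small risk set.

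At stake are the right-hand end of the plot and any median that falls there. Both could contradict the primary proportion computed from the same subjects.

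**Working it through.** **Design figure.** The only stated design figure is 89% power (protocol 14.1, SAP 4.1) for recurrence-free rates of 0.600 and 0.880 with 40 and 80 subjects. The continuity-corrected formula gives 89.2%, and the odds ratio is (0.6/0.4)/(0.88/0.12) = 0.205. Both reproduce. The planning recurrence rates are therefore 40% (sham) and 12% (FAI). No figure is stated for time to recurrence.

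**Direction.** With S = product of (1 - d/r) over event days, where d is the number of events and r the number at risk, earlier censoring leaves every d unchanged and can only lower r. The curve under the SAP rule is therefore at or above the common cut-off curve in every data set. Before Day 152 (or Day 332) the two are identical.

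**Worked example.** Event-free visits are spread evenly over Days 160-200 (an assumption).

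| Arm | Events: before Day 152 / Day 180 / Day 195 | SAP rule, S at end | Common censoring at Day 208, S at end |
|---|---|---|---|
| Sham, n=40 | 12 / 2 / 2 | 28/40 × 14/16 × 4/6 = 0.408 | 28/40 × 26/28 × 24/26 = 0.600 |
| FAI, n=80 | 6 / 2 / 2 | 74/80 × 38/40 × 10/12 = 0.732 | 74/80 × 72/74 × 70/72 = 0.875 |

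In the sham arm 16 of 40 subjects (40%) recurred, but the SAP rule shows 59% and a median of Day 195. In the FAI arm it shows 27% instead of 12.5%.

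**Analytic check, no unscheduled visits.** Assume four looks (Days 28, 60, 90 and the subject's own Month 6 visit) with equal detection probability p, and distinct visit days.
- Sham: p = 1 - 0.6^(1/4) = 0.120. Before the last look S = 0.6^(3/4) = 0.682, with about 27 at risk.
- FAI: p = 1 - 0.88^(1/4) = 0.0315. Before the last look S = 0.88^(3/4) = 0.909, with about 73 at risk.
- Under the SAP rule the expected last-look factor is the product of (1 - p/k) for k = 1 to n: 0.619 (sham) and 0.857 (FAI). It should be 1 - p.
- Recurrence at Day 208: 1 - 0.682 × 0.619 = 58% instead of 40%, and 1 - 0.909 × 0.857 = 22% instead of 12%.

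**Simulation at the planning rates.** Visit spread and detection pattern are assumptions, and no missing data are assumed. Model A is the four-look model with visit SD 10 days. Model B has a constant hazard, visits with SD 10 days or uniform over the window, and 0-50% of recurrences found at unscheduled visits. Each cell gives the SAP rule, then the common cut-off.

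| 6-month analysis | Model A | Model B |
|---|---|---|
| Sham, Day 208 | 57% vs 40% | 68-74% vs 40-43% |
| FAI, Day 208 | 21% vs 12% | 28-37% vs 12-13% |
| Sham, Day 180 | 37.4% vs 36.0% | 33.5-37.2% vs 31.0-35.4% |
| FAI, Day 180 | 11.3% vs 10.8% | 9.9-11.2% vs 8.9-10.5% |
| Sham median reached (share of trials) | 57% vs 13% | 82-86% vs 13-21% |
| FAI median reached (share of trials) | about 6% vs 0% | 11-25% vs 0% |

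In Model A, 43% of trials reached a sham median with fewer than half of the arm recurred. In Model B with no unscheduled visits at all, the sham curve still ends at 73% instead of 40%. Run scenario by scenario, the Day 180 difference is 0.5 to 2.5 points.

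**12-month analysis (Model B).** The curve at Day 388 is 82% vs 66% (sham) and 44% vs 23% (FAI). The sham median is unchanged in 98% of trials, at about Day 270. The FAI median is reached in 28% of trials under the SAP rule and in none under the common cut-off.

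**The case against.** The strongest reply is that little of what is reported depends on the tail. The endpoint is descriptive, no test or hazard ratio uses it, and the proportions are tabulated separately. The 30-day grid puts Month 6 at Day 180, where the effect is small. A sham median first reached inside the window typically rests on about five subjects. The 12-month curve keeps event-free subjects at risk through Days 152-208, so the Month 6 artefact disappears from it, and only each curve's last window is wrong. All of this stands. It limits the importance but does not remove the error, because SAP 8.2 also commits to plots and to medians with confidence intervals.

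The sizes depend on the model, as the gap between the two models shows. Only the direction is free of these assumptions.

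Another reply is that censoring at the last event-free examination is conventional. That works when events are counted to the same point for each subject, which is not so here. It is fair, though, that a Day 208 cut-off treats the days after a subject's visit as event-free unless a recurrence is reported.

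A reader might infer more than the documents support:
- *That the whole curve and both medians are overstated.* The curve before the window is unchanged, and a median changes only if the curve crosses 50% inside the window.
- *That the tabulated Month 6 point is too low, because about 37% at Day 180 is below 40%.* This compares two reading days. Compared at Day 180, the SAP rule is slightly higher.
- *That a median should be shown only if half of the arm has recurred.* This is not a valid rule. With legitimate censoring, a Kaplan-Meier median can be sound with fewer observed events.

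**Conclusion.** The concern holds for the end of each curve. The cut-offs for events and censoring differ, and no section reconciles them. SAP 11.2 records that the event windows in 8.1 and 8.1.1 were clarified after unmasking, but it lists no matching change to 8.2.

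The upward direction inside the closing window is certain in both arms. The size rests on the planning rates, the assumed visit spread and detection pattern, and complete data. Under those assumptions the 6-month curve ends about 17 to 33 points too high for sham and about 9 to 24 points too high for FAI. The median most exposed is the 6-month sham median. The 12-month sham median is rarely affected. The FAI median is usually not reached, but at the planning rates any 6-month value reported for it would be spurious. The 36-month rule has the same mismatch; its size was not calculated.

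The primary chi-square test uses proportions and is untouched. This should be corrected, but it does not threaten the trial's main conclusion.

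**What to change.** Use one cut-off for events and censoring in SAP 8.2. Either option works for Months 6 and 12:
- Place scheduled-visit events and censoring on the nominal visit day, or use an interval-censored (Turnbull) estimate.
- Or censor event-free subjects still in follow-up at Day 208 or Day 388, and those who leave earlier at their last examination. With complete status the end-of-window estimate then equals the crude proportion.

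At Month 36, where follow-up ends, use the nominal day or the interval-censored estimate. Read the end-of-period estimate at the end of the window rather than at Day 180 or its later equivalents. State the event date for recurrences imputed for missing data; a date late in the window would worsen the drop under the present rule. Add no condition that half of the arm must have recurred before a median is shown.

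The cost is a few sentences, one derived variable (more programming for the interval-censored estimate) and no new data. The common cut-off has one drawback: unexamined days between the visit and Day 208 count as event-free unless a recurrence is reported. SAP 4.2.1 unmasks the sponsor and the biostatistics team after the Month 6 lock, so a change made after that should be recorded in SAP 11.2 as post-unmasking, ideally with both versions shown.

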A higher incidence of anemia (irrespective of relationship to drug) was observed in subjects who received Iluvien compared to sham (3%, sham; 7%, 0.2 μg FA /day; 9%, 0.5 μg FA /day). The cause of this increase is not known and was not considered by the Data Monitoring Safety Board to be related to FA. It has been hypothesized that the increase may be due to the use of oral carbonic anhydrase inhibitors (CAIs) (which occurred more frequently in the active treatment groups). This class of IOP-lowering drugs is known to exacerbate renal dysfunction and possibly compromise erythropoietin production. A post-hoc analysis was performed in which all subjects were categorized with or without anemia and with or without a systemic CAI (administered during or within 90 days of anemia). Based on a Pearson chi-square test, there was a relationship between the use of a CAI and anemia in the 0.2 μg FA /day group (p-value <0.0001, and in the 0.5 μg FA /day group (p=0.0073).

Deaths and Serious Adverse Events

A total of 56 (6%) deaths were reported in the FAME studies. None of the deaths were attributed to study drug or unexpected in the patient population.

A total of 401 (42%) subjects had at least 1 drug-related serious adverse event (SAE), all of which were ocular in nature. The overall incidence of drug-related SAEs was several-fold higher in the Iluvien insert groups relative to sham.

Ocular Adverse Events

In the FAME Studies, the most common drug-related TEAEs were cataract operation (39% of subjects), cataract (36%), increased intraocular pressure (25%), and myodesopsia (8%).

Cataract-Related Events in Phakic Subjects

The FAME studies enrolled 621 subjects with phakic study eyes at baseline; the remaining 335 study eyes were pseudophakic at baseline. The incidence of cataract in the study eye was higher in the active treatment groups [80% (low dose), 88% (high dose)] than in the sham group (46%). The most common types of cataracts in the study eye were cataract (NOS) and posterior subcapsular cataract, both of which were reported more frequently in the active treatment groups than in the sham group. The percentage of phakic subjects who had a cataract operation in the study eye was also higher in the active treatment groups [75% (low dose), 85% (high dose)] than in the sham group (23%).

IOP-Related Events and Procedures

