9.10.2. Prohibited Medications

Other than the exceptions described in [Section 9.10.1](#), [Section 9.12](#) or in this section below, the following concomitant medications are not permitted during the study:

- Oral, systemic, injectable, or topical steroids
- Systemic immunosuppressants

Systemic medications or topical steroids administered as part of gradual dose reduction (tapering), as described in [Section 9.10.1](#), are not considered prohibited medications.

Additionally, topical steroids administered as short term standard treatment following an ocular surgical procedure are not considered prohibited medications.

It is advisable for the PI to discuss treatment with the Medical Monitor before administering any prohibited medication unless it is an emergency.

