7.1.2 Concomitant Medications

Concomitant medications are defined as those medications which are taken on or after the initiation of study treatment (Day 1). This includes medications which start prior to Day 1 but continue while the subject is on treatment.

The total number of concomitant medications and the number and percentages of subjects with at least one concomitant medication will be summarized by treatment group. The number and percentages of all concomitant medications will be summarized by treatment group and by ATC level 1 term, ATC level 2 term, and preferred term. An additional summary of the number and percentage of subjects with at least one concomitant medication for each of the specified reasons for medication (recurrence of uveitis, treatment emergent AE, increased IOP, cataract, other) will be summarized by treatment group and by ATC level 1 term, ATC level 2 term, and preferred term. All summaries will be performed using the Safety population.

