7.1.2.1 IOP Lowering Medication

The number and percentage of subjects requiring IOP lowering medication to control elevated IOP will be summarized by treatment group, eye (study, fellow), and time interval. Any systemic medications will be summarized as received in both the study and fellow eyes. IOP lowering medications will be identified as those medications with a reason for medication of "Increased IOP". Incidence will be summarized overall (through 6, 12 or 36 months) and for 3 month time intervals through 6 or 12 months and 6 month time intervals from 12 to 36 months.

The number of medications (one, two, \geq three) required to achieve adequate IOP control will also be included in the summary. A single medication must be used for a minimum of 7 days. Multiple medications must be used concurrently for a minimum of 14 days.

A summary of IOP lowering medications will also be presented by geographic region (United States, EMEA, and India) and history of incisional surgery to control elevated IOP (History of

Incisional Surgery, No History of Incisional Surgery). All summaries will be performed using the Safety population.

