7.1.3 Systemic/Topical Treatment at Study Entry

If a subject is receiving systemic corticosteroids or immunosuppressants, or topical steroids to control uveitis prior to study enrollment, that subject will have such treatment ended within three months following study Day 1, in a manner that follows the standard of care for ending the specific treatment. For example, some systemic treatment regimens may be ended immediately, while others require a period of gradual dose reduction (tapering). Systemic medications or topical steroids administered as part of gradual dose reductions are not considered prohibited medications. Medications received as such treatments will not be recorded on the concomitant medications page but will be recorded on a separate eCRF page.

The number and percentages of subjects with at least one systemic/topical treatment medication at the time of study entry will be summarized by treatment group. The number and percentages of all medications received as systemic/topical treatments will be summarized by treatment group and by ATC level 1 term, ATC level 2 term, and preferred term. All summaries will be performed using the Safety population.

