8.2. Exploratory Efficacy Endpoints

The proportion of subjects with recurrence in the study eye within 12 and 36 months will be analyzed using the same inferential analysis employing the same methods as for the primary analysis as noted in [Section 8.1.1](#). Sensitivity analysis will also be performed for the proportion of subjects with recurrence in the study eye within 12 and 36 months as noted in [section 8.1.3](#).

The following endpoints will be analyzed for the ITT and PP populations employing descriptive statistics only:

- Proportion of subjects in each treatment group who have a recurrence of uveitis in the fellow eye (within 6 months, within 12 months and within 36 months)
- Mean change from baseline in BCVA letter score in the study eye in each treatment group (at 6 months, 12 months and 36 months)
- Number of recurrences of uveitis in each treatment group (within 6 months, within 12 months and within 36 months)
- Time to recurrence of uveitis in study eye in each treatment group (within 6 months, within 12 months and within 36 months)
- Number of adjunctive treatments required to treat recurrences of uveitis in each treatment group (within 6 months, within 12 months and within 36 months)

- Resolution of macular edema, as measured by OCT imaging (at 6 months, 12 months and 36 months)

Exploratory analyses will use the US/FDA definition of recurrence of uveitis. No missing data will be imputed other than as noted in [Section 8.1.2](#). The data imputation method will be applied to recurrence of uveitis in the fellow eye values in the same manner as the study eye, with the 3rd criteria revised to consider use of prohibited local medications in the fellow eye, instead of the study eye.

The number and percentage of subjects with a recurrence of uveitis in the study eye within 12 months and within 36 months and with a recurrence of uveitis in the fellow eye within 6 months, within 12 months and within 36 months will be presented by treatment group.

ETDRS letter score absolute value and change from baseline at Month 6 (and 12 and 36) will be described for each treatment group using descriptive statistics.

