The number of adjunctive treatments, including systemic steroids or immunosuppressants, intra/peri-ocular steroids, and topical steroids, will be determined using medications/therapies recorded on the Concomitant Medications page with start/end dates within the given time period (6, 12 or 36 months). The number and percentage of subjects by number of adjunctive treatments will be presented by treatment group and category of adjunctive treatment. The intra/peri-ocular steroids and topical steroids will also be presented by eye (study, fellow). Multiple doses of the same medication which are part of one treatment regimen will be counted as one adjunctive treatment for the purposes of analysis.

Resolution of macular edema will be summarized using a shift table comparing the presence (Yes, No, Not Evaluable) of macular edema at Month 6 (and 12 and 36) to the baseline response by eye (study, fellow) and treatment group.

9. Safety Analysis

Safety analyses will be performed on the Safety population at 6, 12 and 36 months. Subjects who are randomized but do not receive treatment will not be included in safety tabulations but have all safety data listed only. Percentages for safety summaries based on the number of subjects with a given event or attribute will be based on the number of subjects who were treated (including sham treatment).

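### SAP 8.2 counts treatments for uveitis recurrence without filtering on the recorded reason, so topical steroids after cataract surgery could inflate the FAI count

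*SAP*

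**What the plan says.** SAP 8.2 names the endpoint as "Number of adjunctive treatments required to treat recurrences of uveitis in each treatment group", to be summarised at 6, 12 and 36 months in the ITT and PP populations. Later in the same section, the counting rule takes treatments "including systemic steroids or immunosuppressants, intra/peri-ocular steroids, and topical steroids" and says their number "will be determined using medications/therapies recorded on the Concomitant Medications page with start/end dates within the given time period". Results are shown by treatment category and, for local steroids, by eye. Repeated doses within one regimen count once.

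Other parts of the plan bear on this:

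- SAP 7.1.2 shows that a reason is recorded for each medication: "specified reasons for medication (recurrence of uveitis, treatment emergent AE, increased IOP, cataract, other".
- SAP 7.1.2.1 uses that field: "IOP lowering medications will be identified as those medications with a reason for medication of" increased IOP. SAP 7.2.1 and 7.2.2 select IOP and cataract surgeries by recorded reason in the same way.
- Protocol 9.10.2 says that "topical steroids administered as short term standard treatment following an ocular surgical procedure are not considered prohibited medications".
- SAP 7.1.3 says that drugs being withdrawn at study entry "will not be recorded on the concomitant medications page but will be recorded on a separate eCRF page", so they are outside this count.
- Protocol 5.3.2.2.2 reports that the percentage of phakic subjects who "had a cataract operation in the study eye was also higher in the active treatment groups": 75% with the low dose and 23% with sham.

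**The concern.** The name of the endpoint and its counting rule do not select the same records. The name limits the count to treatment of recurrences. The rule limits it by drug class, source page and date, and ties no treatment to a reason or to a recorded recurrence. Where the SAP wants a reason filter it writes one, so a programmer working from the text would have grounds to apply none here.

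The records most likely to be swept in are short topical steroid courses after cataract surgery. The protocol exempts these from the prohibited list, and SAP 8.1.2 does not let topical steroids trigger an imputed recurrence in the US/FDA primary analysis. The same course would then be ignored for the primary endpoint and counted here. Because cataract surgery is expected to be commoner with the insert, the extra counts would fall unevenly between arms and make FAI look worse on an endpoint meant to show a reduced need for rescue treatment.

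**Working it through.** **The plan's own figure.** The plan gives no design figure for this endpoint. Its one power statement (89% for the primary test, recurrence-free rates 0.600 and 0.880, 40 and 80 subjects) reproduces at 89.2% with the continuity-corrected normal approximation. Nothing below depends on it.

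**Inputs.**

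- Cataract surgery in phakic study eyes over 36 months: 0.75 (low dose) and 0.23 (sham), from Protocol 5.3.2.2.2. Protocol 5.3.2.2 says the FAI insert has the same release rate as that low-dose product.
- Phakic share in those studies: 621/(621 + 335) = 621/956 = 65%. The documents do not give this trial's share, so 40% to 80% is shown as an assumed range.
- One topical steroid course per operation: an assumption. The SAP's rule that one regimen counts once is consistent with it.

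**Formula.** Expected post-cataract courses per subject = phakic share × surgery rate. Excess in FAI = phakic share × (0.75 − 0.23) = phakic share × 0.52.

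| Phakic share | FAI | Sham | Excess in FAI |
|---|---|---|---|
| 40% | 0.300 | 0.092 | 0.208 |
| 65% | 0.487 | 0.149 | 0.338 |
| 80% | 0.600 | 0.184 | 0.416 |

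At 65% phakic this is 80 × 0.487 = 39 courses in the FAI arm and 40 × 0.149 = 6 in sham. The SAP reports subjects by number of treatments, not means. With one study-eye operation per affected subject, the same figures mean that about 49% of FAI and 15% of sham subjects move up one category in the study-eye topical row.

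**After a reason filter.** Courses coded to cataract or another non-recurrence reason add 0 in both arms.

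**Illustration of leverage, with assumed recurrence treatment rates.** If true recurrence treatments were 0.5 per FAI subject and 1.0 per sham subject, the ratio would move from 0.50 to (0.5 + 0.487)/(1.0 + 0.149) = 0.86 at 65% phakic (0.73 at 40%, 0.93 at 80%). At 0.3 and 0.6 it would be (0.3 + 0.487)/(0.6 + 0.149) = 1.05.

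**Dates.** Section 8.2 refers to start and end dates falling within the period. SAP Section 4 includes, at Months 6 and 12, medications whose start day is no later than the end of the visit window (days 208 and 388), and at Month 36 all data in the database. The two wordings differ, but Section 4 supplies a usable general rule.

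**The case against.** The strongest reply is that Section 8.2 is silent rather than wrong. The endpoint's name already restricts it to recurrence treatment, and a careful programmer could apply the reason field on that basis. This stands in part: a reader might infer that the SAP directs every steroid to be counted whatever the reason, and it does not say so. But it does not state the restriction either, and its explicit filters elsewhere make the silence matter.

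A reader might also infer that systemic steroids for unrelated illness contaminate the count to a similar degree. The documents do not support this. Protocol 9.10.2 prohibits them outside tapering and recurrence treatment. SAP 8.1.2 generally imputes a recurrence when a subject with no previous recurrence takes one, subject to the review of potential impact on efficacy. Counting them is broadly in line with the plan's own convention.

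Nor do the documents show that courses running past a cut-off are dropped. Section 4 answers that for Months 6 and 12 and uses all data at Month 36. What remains is a wording mismatch.

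The contamination is also confined and visible. It falls mainly in the topical row of the operated eye. SAP 7.1.2 tabulates medications by reason, and SAP 7.2.2 tabulates cataract surgery by arm and interval. These tables reveal the problem but do not repair the endpoint: the by-reason table counts subjects with at least one medication in the Safety population, not numbers of treatments in ITT and PP.

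Finally, the surgery rates come from another disease. Sham subjects here receive local steroids first for recurrences (Protocol 9.12), and Protocol 5.2 links all corticosteroid therapy to cataract, so sham surgery may exceed 23%. Each 10 percentage points added to the sham rate lowers the excess at 65% phakic by 0.65 × 0.10 = 0.065 courses.

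**Conclusion.** The point holds and is minor. As written, the rule does not deliver the endpoint it is named for. Applied literally, it is expected to add about 0.34 topical courses per subject more to FAI than to sham by Month 36, or 0.21 to 0.42 over the assumed phakic range. That size rests on surgery rates like those in the diabetic macular edema studies, a phakic share that this trial's documents do not give, and one course per operation. The effect should be smaller at Months 6 and 12, because operations accumulate over time, but the documents give no rates from which to size it there.

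A reader might infer from the illustration that the comparison between arms would reverse. That needs recurrence treatment rates that appear nowhere in the documents, so it shows only that the excess is not negligible beside plausible counts. The endpoint is exploratory and descriptive, the expected bias runs against the insert, and the primary analysis and its power are untouched.

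**What to change.** Amend the counting rule in SAP 8.2 as follows:

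1. Count only medication records whose recorded reason is recurrence of uveitis.
2. Say how treatment of recurrences outside the US/FDA definition is handled. SAP 8.2 applies that definition to the exploratory analyses, and it omits anterior chamber cells. Protocol 13.1 includes them, and Protocol 9.12 has investigators consider topical steroids for cell-only recurrences. The reason code may therefore include treatment of events that are not recurrences under this SAP. Either state that these are included, or link each treatment to a qualifying recurrence.
3. Show all other steroid and immunosuppressant use in a separate row. As the filter is expected to favour the insert, both counts should be visible.
4. Replace the start/end date wording with the start-day rule of SAP Section 4.

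Items 1, 3 and 4 need no new data: one filter on an existing field, one added row and a wording change. Linking treatments to recurrences under item 2 takes some programming; stating the choice costs a sentence. This SAP already records changes made after unmasking in Section 11.2, and this one should be logged there if it is made after the Month 6 lock.
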